6.1.6 Unscheduled Visits

Additional visits may be scheduled, as necessary, to ensure the safety and well-being of subjects. All additional exams should be fully documented in the source documents and on Unscheduled Visit eCRFs, as appropriate. Refer to Section 7.2 for the procedures required should an AE be present at an Unscheduled visit. Visits intended to fulfill scheduled visit requirements that fall outside the designated scheduled visit range are not Unscheduled Visits. In these cases, the visit data will be collected and transcribed to the appropriate scheduled visit eCRFs.

If a subject is seen for multiple visits during a given visit timeframe, the data from the visit that is intended to meet the protocol requirements for the scheduled visit should be captured on the visit eCRF. Where such a determination cannot be made, the first visit within the scheduled visit interval will be used for completion of the protocol required scheduled visit eCRF. Data from any additional visits within a scheduled visit interval will be captured on an Unscheduled Visit eCRF.

Procedures to be followed during an Unscheduled Visit will depend on the reason for the visit:

- a. Indicate the reason for the Unscheduled Visit.
- b. If the subject is experiencing problems, assessments will be performed according to the Investigator's judgement.
- c. If the exclusive purpose of the visit is to dispense study lens/ Study Kit and the subject is not experiencing any problems (refer to Section 6.1.8.).
- d. Collect the following lens wear parameters from the subject:
 - Average daily wearing time (since last visit)
 - Average hours of comfortable wear (since last visit)
 - Hours lenses worn on the day of this visit
 - Did subject replace their lenses? (If so, when)
- e. Complete the Symptoms/Complaints Form (Study Lenses Symptoms/Complaints), including use of rewetting drops
- f. Have the subject complete and initial the Lens Performance Assessment record (Study Lenses Performance Rating Scales).
- g. Collect any relevant medical treatment information, including any adverse events, including whether a culture may have been taken.
- h. If the subject did not come to the visit wearing one or more study lenses, go to Step i. Otherwise, evaluate the lenses (while on eye):

- High contrast distance lens VA
- Over-refraction and distance VA
- Lens wettability
- Lens deposits (type, percent and degree)
- Lens centration
- Lens movement
- For each eye, compare the high contrast distance lens VA to the high contrast distance lens VA obtained at the Screening/Dispensing Visit. If the VA has decreased by 10 letters (0.2 logMAR) or more, explain.
- i. Perform a slit-lamp examination (remove the lenses if the subject wore lenses to the visit). Record and sketch any scars and slit-lamp findings greater than Grade 2 in the subject's source document and transcribe this information to the visit eCRF. If a corneal infiltrate is noted record details according to Corneal Infiltrates, Section 2.0: Slit-Lamp Examination of Appendix B: Methods of Clinical Evaluation.
- j. If a new Study Kit is required, designated site staff will log into RTSM system to dispense a new Study Kit (refer to Section 4.4.2) to the subject according to RTSM notification email and record in the Product Accountability Log.
- k. If an unscheduled lens replacement is required at this visit, dispense a new pair of subject's habitual lenses and collect the following information:
 - Primary (one) reason for replacement
 - Dispensed lens type (brand), sphere power, base curve
 - Distance lens VA
 - Over-refraction and distance VA
 - Lens wettability
 - Lens centration
 - Lens movement
 - For each eye, compare the distance lens VA to the distance lens VA obtained at the Screening/Dispensing Visit. If the VA has decreased by 10 letters (0.2 logMAR) or more, provide an explanation.
- If Study Lenses were replaced, unmasked designee to collect the worn lenses from the subject. All worn lenses will be returned to the Sponsor in lens cases filled with *Bausch* + *Lomb Sensitive Eyes*® *Saline Solution* at the end of the study. Place the lens in a labeled zippered bag.
- m. Unmasked designee to place the lens case in the labeled zippered bag and the used Study Kit (bottle and carton) in the subject's bag. DO NOT seal subject bags until a full accountability is performed by a Clinical Monitor at the end of the study.
- n. All study materials (refer to Sections 4.4.2 and 4.4.3) must be returned to the Sponsor at the end of the study.
- o. If the subject needs to exit the study at this visit,
 - Complete the Exit Visit as per Section 6.1.5.
 - Unmasked designee to collect the Study Kit (bottle and carton) dispensed to the subject.

- Complete the form(s) listed below and transcribe the information to the eCRF as appropriate:
 - Unscheduled Visit Form
 - Exit Visit Form (to be used if the subject is discontinued or exited at this visit)

6.1.7 Missed Visits

Missed Visits will be handled as follows:

a. If a subject misses any scheduled follow-up visit and cannot be seen prior to the start of the visit range for the next scheduled follow-up visit, the visit is considered missed.

6.1.8 **Product Dispensing Only Visit**

Product Dispensing Only Visits will proceed as follows:

- a. If a subject is seen exclusively for resupply or replacement of study materials, a complete exam is not required, as long as the subject is not experiencing any problems. If any assessment is performed, then an Unscheduled Visit Form must be completed (see section 6.1.6).
 - If additional study solution is required at this visit, go to Unscheduled Visit Section 6.1.6, j.
 - If a lens replacement is required, go to Unscheduled Visit Section 6.1.6, k.

6.2 Study Completion / Early Study Terminations / Suspensions

6.2.1 Study Completion

For purposes of the Investigator notifying the IRB, the study is complete when all subjects at the sites have been exited. Sponsor approval is required prior to IRB notification.

6.2.2 Early Study Termination/Suspension

If during the study it becomes evident to the Sponsor that the study should be stopped prematurely or placed on hold, appropriate notification will be given to the Investigator(s), IRBs, and FDA, as applicable. Bausch + Lomb will instruct the Investigators to stop/restart dispensing study materials and will arrange for study closeout, if applicable, at each site.

6.3 **Concomitant Medications/Therapy**

Study subjects are not allowed to use other lens care products, ocular solutions, ocular medications, or eye drops (over-the-counter or prescription) during the study unless specifically approved by the Investigator following consultation with the Sponsor. Use of other contact lenses is not allowed.

Ocular medications, systemic or topical medications that, in the Investigator's opinion, could potentially affect ocular physiology or lens performance are also prohibited, unless medically necessary during the course of the study. If used during the course of the study, these medications must be recorded in the appropriate eCRF.

6.4 Treatment Compliance

Treatment compliance will be assessed using lens wear parameter data.

6.5 **Protocol Deviations**

A deviation from the protocol is an unintended and/or unanticipated departure from the procedures and/or processes approved by the Sponsor and the IRB and agreed to by the Investigator. It is a Sponsor expectation that Investigators will follow the protocol and procedures as written. The Sponsor will not grant protocol waivers for this study. The Investigator may implement a deviation from the protocol to eliminate an immediate hazard to study subjects without prior IRB/EC approval. As soon as possible after such an occurrence, the implemented deviation, as well as the reasons for it should be submitted to the IRB/EC for review and approval. It should also be submitted to the Sponsor for agreement, and to the regulatory authorities, if required.

In the event a protocol deviation occurs, the date of and reason for deviations must be documented in all cases. Significant or major protocol deviations impacting the rights or safety of the subject or the integrity of the study must be reported by the Investigator to the IRB/EC and Medical Monitor immediately. Reporting of all other protocol deviations must adhere to the requirements of the governing IRB/EC. Unless the protocol deviations put the subject at risk or the subject's condition requires that they be discontinued from the study, subjects may continue to participate until the end of the study.

Site Corrective Action Plans will be developed and completed as deemed necessary by the Sponsor, Sponsor Designee (e.g., Contract Research Organization, CRO) for sites or Investigators who deviate from this protocol in a way that adversely affects the rights, safety or well-being of the subject(s) and/or the quality or integrity of data. The Site Corrective Action Plan will outline the deviation and the site's corrective and/or remedial actions. Decisions regarding critical deviations that merit Investigator disqualification and site closure will be made by the Sponsor and documented in the Trial Master File.

7.0 ADVERSE EVENTS

7.1 Introduction to Adverse Event Definitions

AEs, Serious AEs (SAEs), Significant Non-Serious AEs, Non-Significant Non-Serious Adverse Events, Adverse Device Effects and Anticipated Serious Adverse Device Effects are defined in this section and in the Protocol's Glossary.

An AE is any untoward medical occurrence, unintended disease or injury, or untoward clinical signs (including abnormal laboratory findings) in subjects, users, or other persons, whether or not related to the investigational medical device, comparator, or the procedures involved. For users or other persons, this definition is restricted to events not related to investigational medical devices.

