9.8 PUBLICATION OF RESULTS	
10.0 REFERENCES	57

APPENDICES

APPENDIX A:	SCHEDULE OF VISITS AND PARAMETERS	A-1
APPENDIX B:	METHODS OF CLINICAL EVALUATION	.B-1
APPENDIX C:	SUBJECT INSTRUCTIONS	.C-1

GLOSSARY OF TERMS

Adverse Device Effect (ADE)	Adverse event related to the use of an investigational medical device.
	Note 1: This definition includes adverse events resulting from insufficient or inadequate instructions for use, deployment, implantation, installation, or operation, or any malfunction of the investigational medical device.
	Note 2: This definition includes any event resulting from use error or from intentional misuse of the investigational medical device.
Adverse Event (AE)	Untoward medical occurrence, unintended disease or injury, or untoward clinical signs (including abnormal laboratory findings) in subjects, users or other persons, whether or not related to the investigational medical device and whether anticipated or unanticipated.
	Note 1: This definition includes events related to the investigational medical device.
	Note 2: This definition includes events related to the procedures involved.
	Note 3: For users or other persons, this definition is restricted to events related to the use of investigational medical devices.
Anticipated Serious Adverse Device Effect (ASADE)	Anticipated serious adverse device effect is an effect which by its nature, incidence, severity or outcome has been identified in the risk assessment.
Device Deficiency	Inadequacy of a medical device with respect to its identity, quality, durability, reliability, usability, safety or performance.
	Note 1: Device deficiencies include malfunctions, use errors, and inadequacy in the information supplied by the manufacturer including labelling.
	Note 2: This definition includes device deficiencies related to the investigational medical device.
Investigational Medical Device	A medical device being assessed for clinical performance, effectiveness, or safety in a clinical investigation
	Note 1: This includes medical devices already on the market that are being evaluated for new intended uses, new populations, new materials or design changes.
	Note 2: This includes medical devices already on the market that are being evaluated within their intended use in a post-market clinical investigation (interventional or non-interventional).
	Note 3: The terms "investigational medical device" and "investigational device" are used interchangeably.

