Life-threatening Adverse Event	An adverse event is considered "life-threatening" if, in the view of either the Investigator or Sponsor, its occurrence places the patient or subject at immediate risk of death. It does not include an adverse event or suspected adverse reaction that, had it occurred in a more severe form, might have caused death.

Medical Device	An instrument, apparatus, implement, machine, appliance, implant, reagent for in vitro use, software, material or other similar or related
	article, intended by the manufacturer to be used, alone or in combination, for human beings, for one or more of the specific purpose(s) of:
	 diagnosis, prevention, monitoring, treatment or alleviation of disease;
	 diagnosis, monitoring, treatment, alleviation of or compensation for an injury;
	• investigation, replacement, modification, or support of the anatomy or of a physiological process;
	 supporting or sustaining life;
	• control of conception;
	• disinfection of medical devices;
	• providing information by means of in vitro examination of specimens derived from the human body; and does not achieve its primary intended action by pharmacological, immunological or metabolic means, in or on the human body, but which may be assisted in its intended function by such means.
Malfunction	Failure of a medical device to perform in accordance with its intended purpose when used in accordance with the instructions for use or clinical investigation plan.
Product Complaints	Any oral, electronic, or written communication that alleges deficiencies related to the identity (labeling), quality, durability, reliability, safety, effectiveness, or performance of a marketed product, including failure of the product, labeling or packaging to meet specifications, whether or not the product is related to or caused the alleged deficiency. A complaint may allege that an adverse event or medical device malfunction has occurred.
Serious Adverse Device Effect (SADE)	Adverse device effect that has resulted in any of the consequences characteristic of a serious adverse event.
Serious Adverse Event (SAE)	An adverse event that led to any of the following outcomes:
	• death
	• serious deterioration in the health of the subject, users, or other persons as defined by one or more of the following:
	 a life-threatening illness or injury, or
	 a permanent impairment of a body structure or a body function including chronic diseases, or
	 in-patient or prolonged hospitalization, or

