7.1.1 Serious Adverse Event (SAE) Definitions

An AE that (related or not related to the investigational test articles, comparator products or study procedures):

• Led to death

- Led to serious deterioration in the health of the subject, that resulted in:
 - A life-threatening illness or injury; or
 - A permanent impairment of a body structure or a body function (e.g., blindness); or
 - Inpatient or prolonged hospitalization; or
 - Medical or surgical intervention to prevent life-threatening illness or injury or permanent impairment to a body structure or a body function
- Led to fetal distress, fetal death, or a congenital abnormality or birth defect.

Note: A planned hospitalization for a pre-existing condition, or a procedure required by the protocol, without serious deterioration in health, is not considered an SAE.

Serious adverse events may include but are not limited to any hazardous, sight-threatening conditions occurring after exposure to the investigational test article or control product including, but not limited to, the following:

- A presumed infectious ulcer (defined as a progressive erosion of the corneal tissue). For the purposes of reporting, this includes:
 - Central or para-central location
 - Penetration of Bowman's membrane
 - Infiltrate $\geq 2 \text{ mm diameter}$
 - Associated with iritis
 - Associated with any increase in intraocular pressure
 - Culture positive for microorganisms
 - Increasing size or severity at subsequent visits

NOTE: Signs of a presumed infectious corneal ulcer may include irregular focal infiltrates, active lesions with raised edges, significant diffuse infiltration, anterior corneal to mid-stromal involvement, erosion with overlying staining, conjunctival and lid edema, anterior chamber reaction (iritis), and severe bulbar and limbal redness. Symptoms associated with a presumed infectious ulcer (microbial keratitis) may include pain of rapid onset, severe redness, purulent or mucopurulent discharge, tearing, and photophobia.

- Any central or paracentral (within the central 6 mm of cornea) corneal event that results in permanent opacification (such as corneal scar or vascularization)
- Any serious adverse ophthalmic events including hypopyon and/or hyphema
- Any neovascularization within the central 6 mm of the cornea
- Permanent loss of ≥ 2 lines of BSCVA
- All cases of iritis.

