7.1.4 Adverse Device Effect (ADE) Definitions

An adverse device effect (ADE) is an AE that is assessed to be related to the use of an investigational medical device. This definition includes AEs resulting from insufficient or inadequate instructions for use; deployment, implantation, installation, or operation; or any malfunction of the investigational medical device. This definition also includes any event resulting from use error or from intentional misuse of the investigational medical device.

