7.1.6 Severity Definitions

- **Mild:** Subject awareness of a sign or symptom that is easily tolerated, requires no treatment, and does not interfere with subject's daily activities.
- **Moderate:** Subject awareness of a sign or symptom which may be a low level of concern to the subject and may interfere with daily activities but can be relieved by simple therapeutic care.
- Severe: A sign or symptom that interrupts the subject's daily activity and requires systemic therapy or other treatment

7.2 **Procedures for Evaluating Adverse Events**

Throughout the course of this study all efforts will be made to remain alert to reportable AEs. If an AE occurs the first concern will be the safety of the subject and appropriate medical intervention will be made. All SAEs, ocular and systemic, must be recorded and reported as required.

All reportable AEs occurring after signing of informed consent and through the subject's end of participation in the study must be reported. All reportable AEs must be followed until the event resolves or stabilizes. This may imply that follow-up will continue after the subject has left the study, and that additional evaluations may be requested by the Sponsor.

Ocular AEs of possible clinical significance should be photo-documented and shared with the Medical Monitor in electronic form.

[figure not shown]
When evaluating for reportable AEs, the Investigator should refer to the definitions for AEs to determine:

- a) whether the event is serious (refer to Section 7.1.1 and 7.1.2.)
- b) whether the event is severe (refer to Section 7.1.6.)
- c) whether the event is significant (refer to Sections 7.1.2 and 7.1.3.)
- d) whether the event is related to the study device (refer to Section 7.1.5.)

7.2.1 **Procedures for Reporting Serious or Significant Adverse Events**

An AE classified as a SAE or a Significant Non-Serious Ocular AE requires expeditious handling and reporting to the Sponsor to comply with regulatory requirements, as follows:

- The event must be reported to the Medical Monitor (Section 24) within 24 hours of the Investigator's awareness of the event via facsimile/email transmission on a paper SAE or Significant Non-Serious AE Report Form signed by the Investigator.
- The Medical Monitor will email a copy of the form (within 24 hours) to all parties listed below:

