7.2.3 Device Deficiencies: Definition and Reporting Procedures

A device deficiency is defined as an inadequacy of a medical device with respect to its identity, quality, durability, reliability, safety, or performance. Device deficiencies include malfunctions, use errors, and inadequate labeling.

Investigators must evaluate, record, and report any complaints/ deficiencies or malfunctions experienced with the study solution during this trial to the Medical Monitor promptly. The Sponsor and Medical Monitor shall review all device deficiencies and, upon the Sponsor's request, Investigators must supply any additional information related to the safety reporting of a particular event.

Report device deficiencies within 24 hours of knowledge to:

The Medical Monitor will distribute, within 24 hours of knowledge, all device deficiencies to the Sponsor.

The Sponsor shall review all device deficiencies and determine and document in writing whether they could have led to an SAE. In the event of a disagreement between the Sponsor and the Investigator(s), the Sponsor shall communicate both opinions to the reviewing IRB per their established reporting procedures and the health authority.

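### Protocol Section 7.1 and the Glossary give opposite rules for adverse events in users or other persons; followed literally, Section 7.1 could let device-related harm to a non-subject go unreported

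*Protocol*

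**What the plan says.** Section 7.1 opens the safety chapter of the Protocol. It lists the event categories and says they "are defined in this section and in the Protocol's Glossary". It then defines an adverse event (AE) broadly, covering subjects, users and other persons regardless of relationship to the device, and closes with a limit for people who are not subjects: "For users or other persons, this definition is restricted to events not related to investigational medical devices".

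The Glossary entry for Adverse Event starts from the same broad definition, but its Note 3 sets the limit the other way: "For users or other persons, this definition is restricted to events related to the use of investigational medical devices".

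There is a related difference in the definition of a serious adverse event (SAE). In Section 7.1.1 the deterioration criterion reads "Led to serious deterioration in the health of the subject, that resulted in", followed by the list of outcomes. The Glossary criterion reads "serious deterioration in the health of the subject, users, or other persons as defined by one or more of the following".

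**The concern.** The two limits are opposites and apply to the same people. Section 7.1 keeps the unrelated illnesses of a bystander and drops the harm that the solution causes. The Glossary does the reverse. A site cannot satisfy both.

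Exposure of people who are not subjects is foreseeable. The solution is kept and used at home, Appendix C tells subjects to store it where children cannot get at it, and designated site staff collect used bottles and worn lenses. The Glossary's own entry for a serious health threat extends to users and other persons. What is at stake is whether a reaction to an investigational product in such a person enters the safety reporting system.

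**Working it through.** The point involves no figure, so the check sets the definitions side by side and traces what depends on them.

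**Step 1. Who counts under each text**

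| Person and event | Section 7.1, read literally | Glossary, AE Note 3 |
|---|---|---|
| Subject, device-related | AE | AE |
| Subject, unrelated | AE | AE |
| User or other person, device-related | not an AE | AE |
| User or other person, unrelated | AE | not an AE |

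The texts agree on both rows for subjects and disagree on both rows for everyone else.

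**Step 2. Is there a tie-break?** Section 7.1 names itself and the Glossary together and gives no order of precedence. SAP Section 1 says the SAP overrides only the statistical sections of the Protocol, and the SAP does not restate the rule for non-subjects. Nothing settles the conflict.

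**Step 3. What depends on the AE definition**
- Section 7.1.4: "An adverse device effect (ADE) is an AE that is assessed to be related to the use of an investigational medical device". An event that is not an AE therefore cannot be an adverse device effect (ADE).
- Section 7.1.4.1 defines an anticipated serious ADE as a kind of ADE. Section 7.1.4.2 defines the unanticipated serious adverse device effect (USADE) as a kind of AE. Both fall away with the AE.
- Section 7.2.1 attaches the 24-hour report to the Medical Monitor to AEs classed as serious or significant, and the IRB report within 10 working days to USADEs. Under a literal Section 7.1, a device-related event in a non-subject triggers neither.

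**Step 4. Is there another route?** Section 7.2.3 covers complaints, malfunctions, use errors and inadequate labeling, with the instruction "Report device deficiencies within 24 hours of knowledge to" a named recipient. Accidental misuse of the solution by another person might reach the Medical Monitor this way. A reaction in another person with no complaint, malfunction, use error or labeling fault need not.

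**Step 5. Does correcting Section 7.1 close the gap?** Only in part. Even with Section 7.1 corrected, the deterioration criterion in Section 7.1.1 names the subject alone, while the Glossary's covers users and other persons. Serious harm short of death in a non-subject would still be classed differently depending on which text is read.

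**Step 6. Does any analysis change?** No. SAP Section 4.8.1 collects AEs over the subject's own participation and summarises them in the Safety Population, which consists of dispensed subjects. By Step 1, their AE definition is the same in both texts. Sample size, power, margins and the four primary endpoint analyses do not use the definition.

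**The case against.** The best defence is that this is a slip of one word that no careful reader would apply. Limiting bystander events to unrelated ones makes little sense, the preceding sentence of Section 7.1 is inclusive, and the Glossary carries a nearly identical sentence without the *not*. That is probably how the wording arose. The documents do not say so, however, and a safety definition should not rely on each of about 22 sites noticing the slip.

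A second objection is that sites may not work from this sentence. Section 7.2 says "the Investigator should refer to the definitions for AEs to determine" seriousness, severity, significance and relatedness, but its itemised references go to Sections 7.1.1, 7.1.2, 7.1.3, 7.1.5 and 7.1.6, not to the opening paragraph of Section 7.1. Its reporting window is also framed around the subject's consent and end of participation. This stands in part: reporting of events in non-subjects is only lightly provided for under either wording. It limits what the correction can achieve but does not remove the contradiction.

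A reader might infer something stronger: that device-related harm to others *would not* be reported, or that every event in a non-subject is misdirected. The documents do not support this. The Glossary is equally in force and includes these events, its SAE and serious health threat entries name users and other persons, and Section 7.2.3 provides a partial 24-hour route. What can be said is that such harm *could* go unreported where a site follows Section 7.1 to the letter.

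**Conclusion.** The contradiction is real and no text in either document resolves it. On a literal reading of Section 7.1, device-related harm to a non-subject drops out of the AE definition and so out of the ADE and USADE definitions and the expedited reporting tied to them.

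Its reach is narrow. Only people who are not subjects are affected. Such events are assumed to be rare, although the documents give no rate for them. The conclusion also assumes that a site acts on the closing sentence of Section 7.1 rather than on the Glossary, and that the event does not surface as a device deficiency. No result that the trial will report on its subjects depends on the wording. It is best classed as an internal inconsistency of low severity, worth correcting because it sits in the safety section and the correction is cheap.

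**What to change.** 1. In Section 7.1, remove *not* from the closing sentence of the AE definition so that it agrees with Glossary AE Note 3.
2. Align the deterioration criterion in Section 7.1.1 with the Glossary SAE entry, so that both cover the subject, users and other persons. SAP Section 4.8.1.3 repeats the Section 7.1.1 wording and can be aligned at the next revision. Its tables cover subjects only, so no output changes.
3. Notify sites of the corrected definitions.

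The cost is two short text changes and a note to sites. If made as a protocol amendment, they need IRB approval before implementation under Section 9.7. No change to design, data collection on subjects, sample size or analysis is needed.
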